16.1.2.1. Adverse Events

All analyses of AEs will be based on the principle of treatment emergence. An AE is considered to be treatment emergent if it has an onset date on or after the date of first dosing, or if it was present prior to the first dose and subsequently worsened. Incidences of all AEs will be presented by system organ class and preferred term by treatment group and overall active group. In addition, incidence of all AEs by severity, by relationship to study treatment, and by relationship to LP procedure will be presented. Data after subjects started symptomatic PD medications will be analyzed both ways (included and excluded).

CONFIDENTIAL

The information contained herein may not be used, disclosed, or published without the written consent of Biogen MA Inc.

16.1.2.2. Clinical Laboratory Results

Clinical laboratory evaluations include hematology, blood chemistry, and urinalysis. Analyses of clinically significant abnormalities, shifts from baseline to post-baseline relative to the normal range, as well as change from baseline by visit will be presented by treatment group and overall active group.

16.1.2.3. Vital Signs

The analysis of vital signs will focus on clinically relevant abnormalities, which will be defined in more detail in the statistical analysis plan (SAP). Incidence of clinically relevant abnormalities in vital signs will be summarized by treatment group and overall active group.

16.1.2.4. Electrocardiogram

The analysis of ECGs will focus on clinically relevant abnormalities, which will be defined in more detail in the SAP. ECG changes from baseline will be summarized using descriptive statistics and presented by treatment group, overall active group, and timepoint.

16.1.2.5. Physical and Neurological Examinations

Abnormal findings during physical and neurological examinations will be recorded as AEs and will be reflected in the summary of AEs.

16.1.2.6. Columbia Suicide Severity Rating Scale

C-SSRS data will be summarized using descriptive statistics and presented by treatment group and overall active group.

16.1.2.7. Magnetic Resonance Imaging

Subjects' brain MRIs will be categorized by normal and abnormal. Shift tables for MRI results will be presented by visit for each treatment group and overall active group.

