8.2. Exclusion Criteria

Candidates will be excluded from study entry if any of the following exclusion criteria exist at Screening, or at the timepoint specified in the individual criterion listed:

Medical History

1. History of or positive test result at Screening for human immunodeficiency virus (HIV). The requirement for testing at Screening may be omitted if it is not permitted by local regulations.
2. History of, or positive test result at Screening for, hepatitis C virus antibody (HCVAb).
3. Current hepatitis B infection (defined as positive for hepatitis B surface antigen [HBsAg] and/or total hepatitis B core antibody [anti-HBc]). Subjects with immunity to hepatitis B from previous natural infection (defined as negative HBsAg, positive anti-HBc, and positive hepatitis B surface antibody [anti-HBs]) or vaccination (defined as negative HBsAg, negative anti-HBc, and positive anti-HBs) are eligible to participate in the study.
4. Presence of freezing of gait.
5. MoCA score < 23 or other significant cognitive impairment or clinical dementia that, in the opinion of the Investigator, would interfere with study evaluation.
6. Unstable psychiatric illness, including psychosis, suicidal ideation, or untreated major depression within 90 days before Screening, as determined by the Investigator.
7. History or Screening MRI results showing evidence of structural abnormalities that could contribute to the subject's clinical state, or any finding that might pose a risk to the subject, or might prevent a satisfactory MRI assessment for safety monitoring. MRI results will be reviewed by a central reader to confirm eligibility at Screening.

CONFIDENTIAL

The information contained herein may not be used, disclosed, or published without the written consent of Biogen MA Inc.

8. History of drug or alcohol abuse within the past 5 years (as defined by the Investigator), a positive urine drug test, or an unwillingness to abstain from these substances during clinic visit days. Subjects who test positive for cannabinoids due to occasional marijuana use, as determined by the Investigator, and who agree to refrain from using marijuana for the duration of the study may be enrolled at Investigator's discretion, after a consultation with the Sponsor. The use of cannabinoids other than marijuana (e.g., cannabinoid cream or gel) is acceptable, unless the use is considered to be drug abuse by the Principal Investigator, which is exclusionary.

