14.1. Clinical Safety Assessments

The following clinical assessments will be performed to evaluate the safety profile of BIIB054:

- AE and SAE recording.
- Physical and neurological examinations performed by the Investigator, Subinvestigator, or qualified designated personnel.
- Columbia Suicide Severity Rating Scale (C-SSRS).
- Vital sign measurements: temperature, pulse rate, SBP, DBP, and respiratory rate will be measured after the subject has been resting in a supine position for at least 10 minutes. Orthostatic vital sign measurements will be obtained whenever blood pressure is read, in the following manner: after supine blood pressure and pulse rate are measured, the subject should stand, and blood pressure and pulse rate should be measured after standing 1 minute and 3 minutes.

To determine eligibility at the Screening Visit, after a 10-minute rest period, the supine SBP/DBP and pulse reading should be performed 3 separate times, at least 15 minutes apart, with the last supine measurement followed by 1 orthostatic SBP/DBP and pulse measurement each at 1 minute and 3 minutes after standing. At subsequent visits, supine vital signs need to be measured only once, followed by orthostatic vital sign measurements at 1 and 3 minutes after standing.

- Weight measurements.
- 12-lead ECGs must be performed after the subject has been resting in a supine position for at least 10 minutes. The ECGs will be read by the Investigator at collection. Copies of all raw ECG data must be made available to Biogen.
- Concomitant therapy and procedure recording.

CONFIDENTIAL

The information contained herein may not be used, disclosed, or published without the written consent of
Biogen MA Inc.

[figure not shown]
[figure not shown]
- Brain MRI safety findings (may include T1, fluid-attenuated inversion recovery, and gradient echo) or other modalities and sequences (to be detailed in the Imaging/MRI Manual). MRI results will be read by the local radiologist at collection and then sent within 24 hours to a central reader for further evaluation and to confirm eligibility at Screening.

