15.1. Definitions

15.1.1. Adverse Event

An AE is any untoward medical occurrence in a patient or clinical investigation subject administered a pharmaceutical product and that does not necessarily have a causal relationship with this treatment. An AE can therefore be any unfavorable and unintended sign (including an abnormal laboratory finding), symptom, or disease temporally associated with the use of a medicinal (investigational) product, whether or not related to the medicinal (investigational) product.

Determination of whether an abnormal laboratory value, vital sign result, MRI result, physical/neurological examination finding, and/or ECG result meet the definition of an AE will be made by the Investigator. Abnormal results are not considered AEs unless 1 or more of the following criteria are met:

- The result meets the criteria for an SAE.
- The result requires the subject to receive specific corrective therapy.
- The result is considered by the Investigator to be clinically significant.

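### The only dedicated brain MRI safety display, a normal/abnormal shift table, cannot show worsening in a subject already abnormal at Screening, so findings below the adverse-event threshold have no stated comparison by treatment group

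*Protocol*

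**What the plan says.** Section 16.1.2.7 of the protocol contains two sentences. The first says that subjects' "brain MRIs will be categorized by normal and abnormal". The second says "Shift tables for MRI results will be presented by visit for each treatment group and overall active group". It names no other MRI summary, and it does not say whether the local or the central read supplies the label.

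Section 14.1 lists among the clinical safety assessments "Brain MRI safety findings (may include T1, fluid-attenuated inversion recovery, and gradient echo", with other sequences possible. Each scan is read locally and then by a central reader. The Schedule of Activities repeats the scan after Screening at Weeks 24, 52, 96 and 148.

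Exclusion criterion 7 (Section 8.2) begins "History or Screening MRI results showing evidence of structural abnormalities that could contribute" to the clinical picture. It goes on to cover findings that might be a risk to the subject or might spoil MRI safety monitoring. Other abnormal scans are not excluded.

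MRI also enters through adverse events. Section 15.1.1 leaves to the investigator the "Determination of whether an abnormal laboratory value, vital sign result, MRI result, physical/neurological examination finding, and/or ECG result meet the definition of an AE". An abnormal result is not an adverse event unless it meets the serious criteria, needs specific corrective therapy, or satisfies the third condition: "The result is considered by the Investigator to be clinically significant". Section 16.1.2.1 counts an event as treatment emergent if it starts on or after first dosing, "or if it was present prior to the first dose and subsequently worsened", and adds: "Incidences of all AEs will be presented by system organ class and preferred term by treatment group and overall active group".

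**The concern.** A two-category shift table has one cell for worsening, normal to abnormal. A subject who starts as abnormal cannot enter it, whatever later scans show. Subjects are aged 40 to 80 at entry, and criterion 7 admits incidental abnormalities that are not exclusionary, so that row need not be empty. For subjects who start normal, the table records that something changed but not what.

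At stake is the use made of scans that are already being acquired and centrally read. A change too minor to be called an adverse event, but more frequent at one dose than on placebo, would be invisible in subjects abnormal at Screening and unspecified in the rest.

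**Working it through.** There is no protocol figure to reproduce, because Section 16.1.2.7 rests on no stated rate or precision. The check has a logical part and an illustrative calculation.

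**Where a new finding would appear**

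| Screening scan | Finding on a later scan | Shift table (16.1.2.7) | Adverse event tables (15.1.1, 16.1.2.1) |
|---|---|---|---|
| Normal | New, at or above the adverse-event threshold | Normal to abnormal, type not shown | Yes, by preferred term and arm |
| Normal | New, below the threshold | Normal to abnormal, type not shown | No |
| Abnormal | New or worse, at or above the threshold | Abnormal to abnormal | Yes, by preferred term and arm |
| Abnormal | New or worse, below the threshold | Abnormal to abnormal | No |

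The last row has no comparative display in the visible text. The second row has one, without the type of finding.

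**Size of the effect on the shift table**

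- Arm size: 101 for placebo, 1250 mg and 3500 mg, and 54 for 250 mg (Table 9, before drop-outs).
- Share abnormal at Screening: not in the protocol. Assumed 30%, 50% or 80%.
- Subjects able to shift, m = 101 × (1 − share), rounded down: 70.7 gives 70, 50.5 gives 50, 20.2 gives 20.
- Rate p with an 80% chance of at least one visible shift: 1 − (1 − p)^m = 0.80, so p = 1 − 0.20^(1/m).

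| Share abnormal (assumed) | m | p |
|---|---|---|
| 0% | 101 | 1.6% |
| 30% | 70 | 2.3% |
| 50% | 50 | 3.2% |
| 80% | 20 | 7.7% |

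Rounding 70.7 up to 71 gives 2.2%, which changes nothing of substance.

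The same effect can be read as a probability. With a true new-finding rate of 2%, the chance of at least one visible shift is 1 − 0.98^m: 0.87 for m = 101 and 0.33 for m = 20.

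**Pooled active column**

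Section 16.1.2.7 also requires the overall active group, 54 + 101 + 101 = 256. With 50% abnormal, m = 128 and p = 1 − 0.20^(1/128) = 1.2%, against 3.2% in one arm of 101. Pooling recovers much of the detection but cannot show whether the rate differs by dose.

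**The case against.** A reader might infer from Section 16.1.2.7 that MRI safety as a whole is reduced to this table, and that a subject abnormal at Screening can never register a new finding. The documents do not support that. Sections 15.1.1 and 16.1.2.1 make a serious, treated or clinically significant MRI result an adverse event, count worsening of a pre-existing condition, and tabulate by preferred term and arm. None of this depends on the Screening category. A conspicuous new lesion, seen by a local radiologist and then a central reader, would probably be reported this way. This part of the objection stands and sets the limit of the point.

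Nor does the protocol name any particular lesion as an expected risk of the antibody; the 26-week rat study it summarises found no gross or microscopic lesions. This also stands, and it is why the types of finding should not be fixed here.

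The protocol does not define abnormal. If the label were kept for clinically relevant findings, few enrolled subjects might carry it, and the 30%, 50% and 80% shares have no source in the documents. This stands too: the figures illustrate and do not estimate.

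It can be said that table layout belongs in the SAP, which is not at hand, and that Section 16.1.2.7 does not bar further tables. That is only partly persuasive. Sections 16.1.2.3 and 16.1.2.4 send their abnormality definitions for vital signs and ECG to the SAP, whereas the MRI section fixes its two categories and makes no such reference. The laboratory section (16.1.2.2) does not refer to the SAP either, but it already plans clinically significant abnormalities, shifts and change from baseline.

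Finally, parts of the imaging and statistical text are blacked out, so the absence of another display can be stated only for the visible text.

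**Conclusion.** The point holds in a limited form. The shift table is blind to worsening in subjects abnormal at Screening and silent on the type of change in the others. What is lost is a systematic comparison, by visit and treatment group, of new or worsened findings below the adverse-event threshold. Capture of serious, treated or clinically significant findings is not affected.

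The size cannot be fixed from the protocol. The increase in the detectable rate worked out above depends on the assumed share of abnormal Screening scans, on a single arm at its Table 9 size, and on the shift table being the only source. It says nothing about the sensitivity of the adverse event tables. This is an inexpensive improvement to a safety display, not a flaw that puts the overall safety evaluation in doubt.

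**What to change.** Keep the shift table and add a sentence to Section 16.1.2.7, for example: The number and percentage of subjects with at least one new or worsened finding relative to the Screening MRI, as judged by the central reader, will be presented by type of finding, visit, treatment group and overall active group; the types of finding will be defined in the SAP.

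This gives every subject with a later scan a way to contribute, whatever the Screening category. It shows what changed and names the read on which the table rests.

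The cost is one more table and a field on the central read form for new or worsened since Screening. The scans are already sent to the central reader, so no extra scans or readers are needed.

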16.2. Pharmacodynamics – Imaging Analyses

16.2.1. Analysis Population

The pharmacodynamic population is defined as a subset of the intent-to-treat (ITT) population with at least 1 post-baseline pharmacodynamic measurement. The ITT population is defined in Section [16.5.2.1](#).

CONFIDENTIAL

The information contained herein may not be used, disclosed, or published without the written consent of Biogen MA Inc.

16.2.2. Methods of Analysis

Year 1 (placebo-controlled portion of the study):

The pharmacodynamic effects of BIIB054 on the integrity of nigrostriatal dopaminergic nerve terminals will be evaluated via DaT/SPECT imaging. The main DaT/SPECT outcome of interest are the change from baseline to Week 52 in the putamen ipsilateral to the clinically affected side SBR, putamen SBR, striatum SBR, and caudate SBR. The change in SBR will be analyzed using the mixed model for repeated measures (MMRM). The model may include the fixed effect of the treatment group, baseline DaT/SPECT values, baseline MDS-UPDRS I + II + III total score value, and visit. The model may include interaction terms between baseline MDS-UPDRS total score and visit, between baseline DaT/SPECT values and visit. Correlation among repeated measures within subject will be considered in the model. The multiple comparison procedure-modelling (MCP-MOD) method may be used to assess and model dose-response.

Years 2 through 4 (active-treatment dose-blinded portion of the study):

Descriptive statistics will be used to summarize the change from study baseline in DaT/SPECT imaging SBR to Week 96/148 by treatment group. Exploratory statistical comparisons may be made to evaluate the impact of immediate versus delayed initiation of BIIB054, with applicable statistical methods.

Missing data due to the impact of the COVID-19 public health emergency will be considered missing at random in the statistical analyses. [REDACTED]

16.3. Pharmacokinetics

16.3.1. Analysis Population

The population for PK analysis is defined as all subjects in the ITT population who have at least 1 measurable BIIB054 concentration in serum [REDACTED]. The ITT population is defined in Section 16.5.1.

16.3.2. Methods of Analysis

Samples for measuring serum [REDACTED] concentration of BIIB054 will be collected as specified in Section 4.2. Serum PK parameters will be calculated by non-compartmental and/or compartmental methods. [REDACTED]

[REDACTED] For Cohort A, PK parameters calculated by a non-compartmental method will also be summarized using descriptive statistics.

Mean serum concentrations of BIIB054 versus time will be plotted by treatment group on both a linear and a logarithmic scale for Cohort A (doses 1 and 3 only). Dose proportionality will be assessed for AUC_{τ} and C_{\max} .

CONFIDENTIAL

The information contained herein may not be used, disclosed, or published without the written consent of Biogen MA Inc.

Atypical serum drug concentrations (such as very low or very high) will be excluded from the analysis if no apparent explanation exists. Concentration observations will also be removed from the data set if corresponding dosing or sampling times are missing or cannot be reconstructed. Concentration data with below limit of quantification value will be removed from analysis. All deletions of data points will be appropriately documented.

Population PK analysis may be conducted to estimate BIIB054 population PK parameters and to identify potential covariates (e.g., demographics, body weight, and anti-BIIB054 mAb) on the variability of BIIB054 PK. Results will be presented in a separate report.

16.4. Immunogenicity Data

16.4.1. Analysis Population

Immunogenicity analysis will be performed for all subjects in the safety population.

16.4.2. Methods of Analysis

The incidence of anti-BIIB054 antibody will be summarized by visit and by treatment group.

16.5. Clinical Function

16.5.1. Analysis Population

The ITT population is defined as all randomized subjects who receive at least 1 dose of study treatment. Data from corresponding dose levels in Cohort A and Cohort B will be pooled for all analyses.

The per protocol population, mainly for the purpose of Year 1 analyses, is defined as a subset of the ITT population who receives at least 70% (10 doses) of study treatment during Year 1 and has not missed consecutive doses.

16.5.2. Methods of Analysis

In general, analyses for clinical function will be done in 2 ways: (1) Year 1 (placebo-controlled portion of the study) and (2) Years 2 through 4 (active-treatment dose-blinded portion of the study) and overall experience (combined data from Years 1 through 4).

In general, all data collected from in-clinic or remote visits will be included in the statistical analyses. The impact of remote assessments on the statistical analyses may be assessed.

Missing data due to the impact of the COVID-19 public health emergency will be considered missing at random in the statistical analyses. Analysis to evaluate the impact of the current COVID-19 emergency and any future public health emergency will be described in the SAP.

CONFIDENTIAL

The information contained herein may not be used, disclosed, or published without the written consent of Biogen MA Inc.

16.5.2.1. Year 1 (Placebo-Controlled Portion of the Study)

The changes in clinical function, including motor [REDACTED] (MDS-UPDRS, [REDACTED]) [REDACTED] outcome measures will be included in the analyses in Year 1 (Week 52).

Analyses of these endpoints will be performed in the ITT population, with select endpoints (e.g., MDS-UPDRS) also analyzed using the per protocol population.

Changes from baseline in the primary endpoint MDS-UPDRS Part I + II + III total scores at Week 52 will be analyzed using the MMRM. The model may include fixed effect of treatment group, baseline MDS-UPDRS I + II + III total score values, region, PD subtype, baseline DaT/SPECT striatum SBR values, visit, and the interaction terms between treatment and visit, between baseline MDS-UPDRS I + II + III total score by visit, and between baseline DaT/SPECT striatum SBR values and visit. The correlation between repeated measures of the outcomes will be taken into consideration in the model. Dose-response relationship will be tested based on the MCP-MOD method (potential candidate models will include linear, linear-log, quadratic, maximum effect (E_{max}), and logistic models, as specified in Section 16.9). A multiple comparison adjustment method will be applied to control the overall type I error at 0.05 in the study, due to the primary endpoint of MDS-UPDRS total score being analyzed at Week 52 and Week 72, and superiority against placebo is considered reached in study if statistically significant result is achieved at either timepoint. The details of the multiple comparison adjustment method will be pre-specified in the SAP. Pairwise comparison of each active group versus placebo will also be conducted, however, no additional multiplicity adjustment will be made, and nominal p-values will be reported.

Secondary endpoints, e.g., change from baseline in the MDS-UPDRS subscores (e.g., Part I, II, or III score, Part II and III total score) will be analyzed in a similar model, but no additional multiplicity adjustment will be made or for other secondary endpoints. Additional details will be provided in the SAP.

[REDACTED]

[REDACTED] Cox's

CONFIDENTIAL

The information contained herein may not be used, disclosed, or published without the written consent of Biogen MA Inc.

proportional hazard model will be used to analyze the data, where appropriate. The model may adjust for baseline MDS-UPDRS values, region, PD subtype, baseline Modified Hoehn and Yahr stage, prior usage status of symptomatic PD medication, and baseline DaT/SPECT striatum SBR values. If the proportionality assumption does not hold, the log rank test will be used. More details will be described in the SAP.

16.5.2.2. Years 2 through 4 (Active-Treatment Dose-Blinded Portion of the Study) and Overall Experience

At Week 72, the primary endpoint of changes from baseline in MDS-UPDRS Part I + II + III total scores will be analyzed using the MMRM, similar to the Year 1 analyses with similar covariates in the model. The treatment groups included in the model will be the delayed start/initiation group (placebo to BIIB054), and the immediate start/initiation groups (the original 250 mg, 1250 mg and 3500 mg BIIB054 groups). Dose response relationship will be tested based on the MCP-MOD method (potential candidate models will include linear, linear-log, quadratic, E_{max} , and logistic models, as specified in Section 16.9). A multiple comparison adjustment method will be applied to control the overall type I error at 0.05 in the study, due to the MDS-UPDRS Part I + II + III total score being analyzed at Week 52 and Week 72 and success of efficacy is considered at either timepoint. The details of the method will be pre-specified in the SAP. The results of the analysis will be considered statistically significant after applying the multiple comparison adjustment method. Pairwise comparison of each immediate start group versus the delayed start group will also be conducted; however, no additional multiplicity adjustment will be made, and nominal p-values will be reported.

Secondary endpoints, e.g. change from baseline in the MDS-UPDRS subparts (e.g., Part I, II, or III, IV score, Part II and III total score) or change in MDS-UPDRS I + II + III total score at end of study, will be analyzed in a similar model, but no additional multiplicity adjustment will be made for secondary endpoints.

[REDACTED]

[REDACTED]

Cox's proportional hazard model will be used to analyze the data where appropriate. The model may adjust for baseline MDS-UPDRS values, region, PD subtype, baseline Modified Hoehn and Yahr stage, prior usage status of symptomatic PD medication, and baseline DaT/SPECT striatum SBR values as appropriate. If the proportionality assumption does not hold, the log rank test will be used. More details will be described in the SAP.

CONFIDENTIAL

The information contained herein may not be used, disclosed, or published without the written consent of Biogen MA Inc.

These outcome measures will be summarized by treatment group.

- [REDACTED]
- [REDACTED]
- [REDACTED]
- [REDACTED]
- [REDACTED]

[REDACTED]

- [REDACTED]
 - [REDACTED]
 - [REDACTED]
- [REDACTED]

[REDACTED]

[REDACTED]

[REDACTED]

[REDACTED]

[REDACTED]

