16.8. Interim Analyses

Safety and PK data only will be reviewed by the IDMC after subjects in Cohort A have completed Week 12 Visit assessments, and before dosing any subjects in Cohort B.

After subjects in Cohort A complete the Week 24 Visit, [REDACTED], all available serum PK, [REDACTED] from [REDACTED] Cohort A will be analyzed by a statistical/PK team independent of the study. The grouped level summary statistics will be reviewed only by a limited number of individuals at Biogen who are not involved in the management of the subjects or subject-level data for the study. No changes to the study design are expected based on this review.

For the purpose of planning for future studies, an administrative interim analysis may be performed when approximately 60% of the subjects have completed the Week 52 Visit. A small unblinded team from Biogen, separate from the study management team, will have access to the unblinded interim analysis results.

A full analysis of the 1-year data will be performed after all subjects have completed the Week 52 Visit. A small unblinded team from Biogen, separate from the study management team, will have access to the unblinded 1-year analysis results.

An interim analysis when all subjects have completed the Week 72 Visit is planned to be conducted. A small unblinded team from Biogen, separate from the study management team, will have access to the unblinded interim analysis results.

A multiple comparison adjustment method will be applied to control the overall type I error at 0.05 in the study, due to the primary endpoint of change from baseline in MDS-UPDRS total score being analyzed at Week 52 and Week 72, and superiority against placebo is considered reached in the study if statistically significant result is achieved at either timepoint at the respective adjusted alpha-level. The details of the multiple comparison adjustment method will be pre-specified in the SAP. No additional multiplicity adjustments will be made for secondary or exploratory endpoint analyses.

CONFIDENTIAL

The information contained herein may not be used, disclosed, or published without the written consent of Biogen MA Inc.

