16.9. Sample Size Considerations

The sample size calculation is based on changes in MDS-UPDRS Part I + II + III total score at Week 52 and at Week 72 of treatment. Based on data from the Parkinson's Progression Markers Initiative study, the placebo subject's mean and standard deviation (SD) at Week 52 and Week 72 are assumed to be 8.0 (10.64) and 9.6 (13.7) respectively. Assuming a maximum of 55% reduction in the change from baseline in the active group with maximum response relative to placebo group, the mean (SD) for this active group will be 3.2 (10.64) and 3.84 (13.7) respectively at Week 52 and Week 72, and the responses for other active groups are assumed to be somewhere between 0 and the maximum response. The primary analysis will be based on the MCP-MOD method to detect a dose-response trend while controlling for multiplicity. Optimal contrasts will be constructed to detect potential dose-response trend under common dose-response curves (e.g., E_{\max} , exponential, logistic, linear in log dose, and quadratic model, which are illustrated with parameters shown in [Figure 5](#) which will be used for both Week 52 and Week 72). The planned enrollment is 311 subjects total (24 subjects in Cohort A and 287 subjects in Cohort B, [Table 8](#)). Actual enrollment is 357 subjects. In Cohort A, 29 subjects were randomized in a 1:1:1:1 ratio to each of the treatment groups, while in Cohort B 328 subjects were randomized in 2:1:2:2 ratio to the placebo, 250 mg, 1250 mg, and 3500 mg groups. Based on the actual enrollment, the estimated number of subjects by cohort and treatment groups are given in [Table 9](#) below. After accounting for dropout rate of 10% and 15% at Week 52 and Week 72, respectively, the estimated sample sizes are given in [Table 10](#) and [Table 11](#). With the updated sample size, the study will provide an average power of approximately 80% to detect the dose-response trend over 1 year of treatment, based on a 2-sided type I error of 0.05 and approximately 73% of power at the Week 72 analyses, based on a 2-sided type I error of 0.05. Overall, the sample size in the study will provide approximately 89% power. If there are any modifications to the candidate dose-response curves/models or parameters, the final candidate models for the MCP-MOD will be prespecified and described in the SAP.

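### A significant MCP-MOD trend test is labelled superiority against placebo, but its 0.05 error rate protects only against a flat dose-response

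*Protocol*

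**What the plan says.** Protocol Section 16.9 names the primary test: "The primary analysis will be based on the MCP-MOD method to detect a dose-response trend while controlling for multiplicity". It gives Week 52 power "to detect the dose-response trend over 1 year of treatment, based on a 2-sided type I error of 0.05". Section 16.5.2.1 attaches the conclusion: "superiority against placebo is considered reached in study if statistically significant result is achieved at either timepoint". Section 16.8 repeats it for the interim looks: "superiority against placebo is considered reached in the study if statistically significant result is achieved at either timepoint at the respective adjusted alpha-level".

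The direct comparisons with placebo are planned but stand outside this rule: "Pairwise comparison of each active group versus placebo will also be conducted, however, no additional multiplicity adjustment will be made, and nominal p-values will be" given.

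The protocol leaves to the SAP how alpha is shared between Weeks 52 and 72 ("A multiple comparison adjustment method will be applied to control the overall type I error at 0.05 in the study") and any change to the candidate models. It does not defer what a significant result means. That is written out in both sections.

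**The concern.** The conclusion named is that BIIB054 is superior to placebo. The null hypothesis to reject for that conclusion is that no dose is better than placebo. The MCP-MOD critical value is set under a narrower null, in which placebo and all three doses have the same mean. Rejecting flatness does not by itself show that a dose beats placebo.

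The two can part because most optimal contrasts for increasing shapes give negative weight to the low dose as well as to placebo. A poor 250 mg result then raises the trend statistic even if 1250 mg and 3500 mg merely match placebo. The study could report superiority against placebo when no dose is better than placebo, and the stated 0.05 would not bound the chance of that.

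**Working it through.** **Inputs.** Week 52 evaluable sizes 91/48/90/90 (Table 10), SD 10.64, and doses 0/250/1250/3500 mg. The illustrative shift is 4.8 points, the planned maximum difference from the printed means (8.0 - 3.2). Candidate shapes come from Section 16.5.2.1 ("potential candidate models will include linear, linear-log, quadratic, maximum effect (E_{max}), and logistic models, as specified in Section 16.9") and Section 16.9 ("E_{\max} , exponential, logistic, linear in log dose, and quadratic model"). Their parameters are in Figure 5, which is not shown, so they were assumed and varied.

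**The plan's own figures.** Section 16.9 states average power of about 80% at Week 52, 73% at Week 72 and 89% overall. Simulation used optimal contrasts, a maximum-statistic critical value found under equal means, and 2-sided 0.05 at each visit. With the 55% effect (0.55 × 8.0 = 4.40; 0.55 × 9.6 = 5.28), one assumed shape set gives 79.9%, 71.6% and, at an assumed between-visit correlation of 0.5, 89.0%. Five sets span 79.9-85.4% at Week 52 and 71.6-78.0% at Week 72. The stated figures are within reach, but an exact reproduction needs Figure 5.

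**Hand check without Figure 5.** The linear contrast depends only on doses and sample sizes: c_i = n_i(d_i - d̄).

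- d̄ = (48×250 + 90×1250 + 90×3500)/319 = 439,500/319 = 1,377.7.
- c = -125,375 (placebo), -54,132 (250 mg), -11,497 (1250 mg), +191,003 (3500 mg). The weight on 250 mg is negative.
- SE = 10.64 × √Σ(c_i²/n_i) = 10.64 × 25,310 ≈ 269,300.
- Count less worsening as positive. If 250 mg is 4.8 points worse and the other doses equal placebo, Z has mean 54,132 × 4.8/269,300 = 0.965.
- Favourable rejection by this contrast alone: 1 - Φ(1.96 - 0.965) = 16.0% at 2-sided 0.05, and 1 - Φ(2.24 - 0.965) = 10.1% at 2-sided 0.025.
- At 3 points worse the mean is 0.603, giving 8.7% and 5.1%.

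**Full maximum-contrast test.** Probability of a favourable Week 52 rejection when no dose is better than placebo:

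| True state | 2-sided 0.05 | 2-sided 0.025 (assumed equal split) |
|---|---|---|
| Flat | 2.5% | 1.25% (half of 0.025) |
| 250 mg worse by 2 points | 4.9-5.8% | 2.7-3.2% |
| 250 mg worse by 3 points | 8-10% | about 4-6% |
| 250 mg worse by 4.8 points | roughly 14-20% | about 9-12% |

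The ranges reflect the assumed shapes. For the last row, one group of five parameter sets ran from 13.1% to 18.7%, and from 7.9% to 12.0% at the split; other sets reached 20%.

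**Adding a comparison with placebo.** Power at Week 52, true maximum difference 4.8, 2-sided 0.05, one assumed shape set:

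| Shape | Favourable trend | plus one nominal pairwise win | plus one Dunnett win (critical value 2.35) |
|---|---|---|---|
| Emax | 89.0% | 88.1% | 82.6% |
| Exponential | 89.7% | 84.0% | 75.0% |
| Logistic | 91.7% | 88.1% | 79.8% |
| Log-linear | 87.6% | 87.3% | 83.5% |
| Quadratic | 88.3% | 86.8% | 80.8% |
| Mean | 89.3% | 86.9% | 80.3% |

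The nominal condition costs 89.3 - 86.9 = 2.4 points on average and leaves a false claim of about 4% when only 250 mg is worse by 4.8 points. The Dunnett condition costs 89.3 - 80.3 = 9.0 points and leaves at most 1.7%. Requiring only a favourable sign leaves average power at 89%.

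**The case against.** The profile needed lies outside the plan's own assumptions. Section 16.9 places the responses of the other active groups between no effect and the maximum, and Section 5.5 expects 250 mg to have minimal efficacy. Nothing in the protocol suggests that the lowest dose would worsen patients while doses 5 and 14 times higher match placebo. The quadratic candidate allows a downturn at high dose, not a harmful low dose. Alpha must also be shared between two visits, so the figures at full 0.05 are upper ones. This is a Phase 2a trial with a dose-response objective, and the pairwise p-values will be reported, so a reader would see if no dose beat placebo. All of this stands, and it is why the gap is modest. It does not make the label correct.

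A reader might also infer that significant harm would count as success, since the rule names a 2-sided test and no direction. Read literally, it would fire about 90% of the time at full 0.05 if every dose were 4.8 points worse. The documents do not support that reading. Superiority already implies benefit, and Section 16.5.2.2 describes the same event as success on efficacy. This needs one clarifying phrase and carries no weight as an error rate.

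**Conclusion.** The point holds as a mismatch between test and conclusion. The 0.05 protects against a flat dose-response and does not bound the error of the claim attached to it. The excess appears only under a non-monotone response with a harmful low dose: roughly 14-20% at full alpha for a 4.8-point deficit at 250 mg, or about 9-12% at an assumed 0.025, against 2.5% and 1.25% when the response is flat. These sizes rest on assumed candidate shapes, normal means, Table 10 sizes and SD 10.64. The direction of the effect does not depend on Figure 5, as the linear contrast shows.

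A reader might go further and infer that the primary test is invalid or its type I error uncontrolled. That does not follow. It is a sound test of the dose-response question in the Section 6 primary objective. Only the conclusion drawn from it is too strong.

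**What to change.** In Sections 16.5.2.1 and 16.8, state that a significant MCP-MOD result in the direction of less MDS-UPDRS worsening, at the alpha allotted to that timepoint, establishes a dose-response signal. Remove the statement that it establishes superiority against placebo, and carry the same wording into the SAP. This costs no power, data or analyses, and also settles the direction.

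If the sponsor wishes to keep a claim of superiority against placebo at Week 52, it should require in addition at least one pairwise comparison with placebo favouring BIIB054, preferably multiplicity-adjusted:

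- **Nominal test:** about 1-4 points of power for most shapes (5.7 under the exponential shape), leaving about 4% error in the 4.8-point scenario. Passing the trend test first does not make adjustment unnecessary, because in that scenario the flat null is already false and the first step gives no protection.
- **Dunnett-adjusted test:** about 9 points of power, with the error below 2.5%.

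The pairwise condition cannot be carried to Week 72. There the comparator is the delayed-start group, already on BIIB054, so no comparison with placebo exists and only the dose-response wording applies.
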